10.1.3 Analyses of Time-to-Event Variables

Time to first achievement of endpoints will only be performed in ITT_A1 up to Week 16. The time to event will be calculated as:

- Time to first achievement (with observed event) = [date of first achievement] – [date of first dose] + 1
- If a subject never attains Endpoint at the end of evaluation period, that subject's time to first achievement will be censored at the last visit where the variable was measured

Time to loss-of-response (and time to relapse) endpoints will only be performed in ITT_B_R Population among those who achieved response at Re-Randomization. The time to failure events will be calculated as:

- Subjects will be considered as failures if they subsequently lost the response, or discontinue from the study due to AE of "Worsening of disease under study," or receive retreatment with risankizumab.
- Time to failure events = [date of failure] – [date of first dose in Part B] + 1
- Subjects who maintain Endpoint throughout the study, or discontinued from the study due to reasons other than above, will be censored at their last measurement.

Both time to first achieving endpoints and time to loss-of-response endpoints will be analyzed using Kaplan-Meier estimates for each treatment group. In the ITT_A1 and ITT_B_R populations, treatments will be compared using stratified Log-rank test.

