7.3.3 Further endpoint analyses

Further endpoints will be summarized, with number and proportion of responders for dichotomous endpoints and mean, median, SD and IQR presented for continuous variables.

Time to onset of *Endpoint*, the time to event will be calculated as:

- Time to first onset (with observed event) = [date of first onset] – [date of first active treatment] + 1
- If a patient never attains *Endpoint* (e.g., PASI75 or PASI90), then that patient's time to first onset will be censored at the last visit where the *Endpoint* was measured (e.g., PASI).

Time to Loss of *Endpoint* will only be performed for patients that are re-randomised at Week 28 (i.e., Arms A and B defined in Section 7.2), where day 0 is defined as the date of the Week 16 visit. Time to loss is defined using the following algorithm:

- a) Never attains *Endpoint* (Failure at day 0)
- b) After achieving *Endpoint*, patient will be a failure if they subsequently do not achieve *Endpoint* and either discontinue from the study or switch therapy while still not achieving *Endpoint*. Time to failure will be calculated using date of first failure to achieve *Endpoint*.
- c) Patients that take prohibited meds to treat Psoriasis will be counted as failures at the time when they first take the prohibited med.
- d) Patients that switch therapy while maintaining response will be censored at their last measurement prior to switching treatment. A switch from active medication to Placebo does not constitute a change in treatment.
- e) Patients who maintain *Endpoint* throughout the study will be censored at their last measurement.

Time to Loss of *Endpoint* (from time of achieving *Endpoint* or from specific point in time) will be defined as above but only for those patients that have achieved *Endpoint*.

All Time to Event endpoints will be presented using Kaplan-Meier curves with comparisons made between treatment groups using stratified Log-Rank test. Further information will be provided in the TSAP.

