7.5 HANDLING OF MISSING DATA

Every effort should be made to collect complete data at all visits.

The following rules will be used to impute for missing data:

- For all non-binary endpoints, last observation carried forward (LOCF) will be used to impute missing values
- For all binary endpoints (i.e. endpoints that are either 1 (patient responded) or 0 (patient did not respond)):
 - If no data after that visit*, then impute as failure (NRI [No Response Imputation])
 - If data at visits* before and after, only impute as success if both visits are successes; else impute as failure

* Patients that take prohibited medications to treat Psoriasis will be treated the same as those that discontinued from the trial – i.e. subsequent visits following start of prohibited medication will be considered as failure for binary endpoints.

Missing items from the PRO questionnaires will be handled according to the measure instructions ([Section 10.7](#)). If there is no data for a particular visit, then it will be imputed following the same rules as described above.

Sensitivity analyses to assess the robustness of the hypothesis testing results will include the following methods where applicable:

- LOCF (for binary endpoints)
- Logistic regression

- Mixed effect Model Repeat Measurement (MMRM) (for continuous endpoints)
- Multiple imputation (for binary endpoints)

Of note, for randomized withdrawal analyses, subjects who received retreatment will be counted as non-responders in all visits after the date of retreatment.

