10.2 STATIC PHYSICIAN GLOBAL ASSESSMENT (SPGA)

The sPGA is a 5 point score ranging from 0 to 4, based on the physician's assessment of the average thickness, erythema, and scaling of all psoriatic lesions ([R15-5200](#)).

The assessment is considered "static", which refers to the patients disease state at the time of the assessments, without comparison to any of the patient's previous disease states, whether at Baseline or at a previous visit.

A lower score indicates less body coverage, with 0 being clear and 1 being almost clear.

Erythema

- 0 Normal (post-inflammatory hyper/hypopigmentation may be present)
- 1 Faint, diffuse pink or slight red coloration
- 2 Mild (light red coloration)
- 3 Definite red coloration (Dull to bright red)
- 4 Bright to Deep red coloration of lesions

Induration (plaque elevation)

- 0 None
- 1 Just detectable (slight elevation above normal skin)
- 2 Mild thickening (slight but definite elevation, typically edges are indistinct or sloped)
- 3 Clearly distinguishable to moderate thickening (marked definite elevation with rough or sloped edges)
- 4 Severe thickening with hard edges (marked elevation typically with hard or sharp edges)

Scaling

- 0 No scaling
- 1 Minimal focal scaling (surface dryness with some desquamation)
- 2 Predominately fine scaling (fine scale partially or mostly covering lesions)
- 3 Moderate scaling (coarser scale covering most or all of the lesions)
- 4 Severe /coarse scaling covering almost all or all lesions (coarse, non-tenacious scale predominates)

Scoring:

Clear	0 = 0 for all three
Almost clear	1 = mean $>0, <1.5$
Mild	2 = mean $\geq 1.5, <2.5$
Moderate	3 = mean $\geq 2.5, <3.5$
Severe	4 = mean ≥ 3.5

sPGA Rating Scale for Overall Psoriatic Disease

Score	Short description	Detailed description
0	clear	No signs of psoriasis. Post-inflammatory hyper/hypopigmentation may be present
1	Almost clear	Normal to pink coloration; Just detectable (possible slight elevation above normal skin) No to minimal focal scaling
2	mild	Pink to light red coloration Mild thickening (slight but definite elevation, typically edges are indistinct or sloped) Predominantly fine scaling
3	moderate	Dull to bright red coloration Clearly distinguishable to moderate thickening Moderate scaling
4	severe	Bright to deep dark red coloration; Severe thickening with hard edges Severe coarse scaling covering almost all or all lesions

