Retreatment: Starting from Week 32, subjects experiencing relapse (defined as an sPGA of ≥ 3), will receive open label risankizumab 150 mg. If this relapse occurs anytime between Week 32 through Week 70, open label risankizumab 150 mg will be administered at 0, 4, and 16 weeks (EOT) after relapse. If this relapse occurs after Week 70 through Week 82, open label risankizumab 150 mg will be administered 0 and 4 weeks (EOT) after relapse. If the relapse occurs after Week 82 through Week 88 the subject will immediately have the EOT procedures performed, including the final dose of study drug.

Follow-Up Period: Subjects who have completed their EOT visit will be followed up for 16 weeks. Follow-up Visit 1 is scheduled at 6 weeks after EOT. And Follow-up Visit 2 is scheduled at 16 weeks after EOT, which is the end of observation (EOO) visit. Subjects who have completed the EOO visit within the specified window, who have not discontinued drug prematurely, and who also meet the eligibility criteria will be offered to roll over into an open label extension study.

Figure 1. Trial Design

BI 655066 is risankizumab.

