10.3.3 Further Efficacy Endpoints

The further endpoints are as follows:

- Achievement of PASI 50 at all visits collected
- Achievement of PASI 75 at all visits collected
- Achievement of PASI 90 at all visits collected
- Achievement of PASI 100 at all visits collected
- Time to the first achievement of PASI 50, PASI 75, PASI 90, and PASI 100
- Time to loss of PASI 50, PASI 75, PASI 90, and PASI 100 response for subjects re-randomized at Week 28
- Change and percent change from baseline in PASI at all visits collected
- Achievement of PASI < 3 at all visits collected
- Proportion of subjects with at least 25% increase in PASI from baseline within 60 days after re-randomization for subjects re-randomized to placebo at Week 28
- Achievement of sPGA of clear or almost clear at all visits collected
- Achievement of sPGA of clear at all visits collected
- Time to the first achievement of sPGA of clear or almost clear
- Time to loss of sPGA of clear or almost clear response for subjects re-randomised at Week 28
- Time to sPGA of ≥ 3 (relapse) for subjects re-randomised at Week 28
- Change from baseline in DLQI at all visits collected

- Achievement of a DLQI score of 0 or 1 at all visits collected
- Achievement of a reduction of 5 or more points from baseline in DLQI score at all visits collected, among subjects with baseline $DLQI \geq 5$
- Change from baseline in HAQ-DI at all visits collected, among subjects with PsA confirmed via ClASsification of Psoriatic Arthritis (CASPAR) and had baseline value > 0
- Achievement of a reduction of 0.3 or more from baseline HAQ-DI at all visits collected, among subjects with PsA confirmed via CASPAR and had baseline value ≥ 0.3
- Change and percent change from baseline on patient Pain VAS, among subjects with PsA confirmed via CASPAR and had baseline value > 0
- Achievement of a reduction of 10 or more from baseline Pain VAS at all visits collected, among subjects with PsA confirmed via CASPAR and had baseline value ≥ 10
- Change and percent change from baseline on patient Global Assessment VAS, among subjects with PsA confirmed via CASPAR and had baseline value > 0
- Change from baseline in Swollen or Tender Joint Count (28 joints) at all visits collected, among subjects with PsA confirmed via CASPAR and had baseline value > 0
- Change from baseline in DAS28 at all visits collected, among subjects with PsA confirmed via CASPAR and had baseline value > 0

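### SAP 10.1.3 records sPGA-triggered retreatment as loss of PASI 50, 75 or 90 even when the threshold is still met, contrary to protocol 7.3.3(d) and not listed in SAP 14.1

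*SAP*

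**What the plan says.** SAP 10.3.3 lists "Time to loss of PASI 50, PASI 75, PASI 90, and PASI 100 response for subjects re-randomized at Week 28" among the further efficacy endpoints. SAP 10.1.3 gives one failure rule for all of them and for relapse: "Subjects will be considered as failures if they subsequently lost the response, or discontinue from the study due to AE of" worsening disease, or if they "receive retreatment with risankizumab". The analysis covers re-randomised patients who had the response at re-randomisation, and "In the ITT_A1 and ITT_B_R populations, treatments will be compared using stratified Log-rank test".

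The trigger is in SAP 4.2: from Week 32, "subjects experiencing relapse (defined as an sPGA of ≥ 3), will receive open label risankizumab 150 mg". No PASI condition is attached. Protocol 10.2 describes the sPGA as "based on the physician's assessment of the average thickness, erythema, and scaling of all psoriatic lesions".

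For the same endpoints, protocol 7.3.3(b) makes a patient a failure only if the endpoint is no longer met. Item (d) adds: "Patients that switch therapy while maintaining response will be censored at their last measurement prior to switching treatment". Protocol 3.1 describes relapse as a switch to open-label drug, so retreatment falls under (d). SAP 14.1, which lists changes from the protocol, does not mention the different event rule.

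For response by visit, protocol 7.5 says that in the randomised-withdrawal analyses "subjects who received retreatment will be counted as non-responders in all visits after the date of retreatment". SAP 10.1.4 does the same under non-responder and multiple imputation.

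**The concern.** PASI multiplies severity by area. The sPGA score is built from three lesion signs and has no area term, although one sentence of protocol 10.2 mentions body coverage. A patient can therefore relapse on sPGA with a few intense lesions and still be well inside PASI 50 or PASI 75. The SAP rule records that patient as having lost the PASI response on the day of retreatment.

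For loss of sPGA 0/1 and for relapse the rule is harmless, because sPGA ≥ 3 is itself the event. For the PASI endpoints it changes the question to loss of PASI X or retreatment, while the label still says loss of PASI X. If withdrawal raises relapse, curves labelled as PASI loss will partly show relapse, most of all at the lower thresholds. The protocol and the SAP also define the event in opposite ways, and a reader of SAP 14.1 would not learn this.

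**Working it through.** **1. The plan's own figure.** No sample size is given for the time-to-loss endpoints. Protocol 7.7 sizes the withdrawal comparison on 90% versus 75% sPGA response at Week 52, 1:2, two-sided 0.05, 90% power. The pooled rate is (0.90 + 2 × 0.75)/3 = 0.80, and

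n(active) = [1.960·√(1.5 × 0.80 × 0.20) + 1.282·√(0.90 × 0.10 + 0.75 × 0.25/2)]² / 0.15² ≈ 101.3, so 102.

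This gives 102:204 = 306 re-randomised, and 306/0.8 = 382.5, so 383. The protocol's figures reproduce. With 400 in the initial active arm, 400 × 0.8 = 320 are re-randomised, about 107:213.

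**2. Can PASI response be held at sPGA ≥ 3?** Score 3 needs a mean of at least 2.5 over three signs (protocol 10.2), hence an integer sum of at least 8. If those item scores carry over to PASI (an assumption), the smallest PASI with area score 1 is region weight × 8 × 1 (protocol 10.1). Baseline 12 is the entry minimum; baseline 20 is an assumption.

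| Region affected | PASI | Reduction from 12 | Reduction from 20 |
|---|---|---|---|
| Head | 0.8 | 93% | 96% |
| Upper limbs | 1.6 | 87% | 92% |
| Trunk | 2.4 | 80% | 88% |
| Lower limbs | 3.2 | 73% | 84% |
| All four | 8.0 | 33% | 60% |

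PASI 75 can be held in limited disease. PASI 50 can be held more widely, but with all four regions affected only from a baseline of 8.0/0.5 = 16. PASI 90 can be held only in limited disease; at baseline 12, only with the head alone affected. PASI 100 cannot be held, because lesions are present and PASI exceeds 0.

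**3. What the log-rank test then does.** The simulation used 107:213 patients, four strata (35/30/20/15%, assumed), the six visits from Week 32 to Week 52, 2,000 runs per case, and independent loss and retreatment times with constant per-visit hazards. PASI loss q is the same in both arms. Retreatment by Week 52 is set at 10% versus 25%, borrowed from protocol 7.7. Those figures are for loss of sPGA 0/1, which includes sPGA 2, so they are probably an upper bound for sPGA ≥ 3. f is the share of retreated patients still holding the threshold. Expected recorded events under the SAP rule are 1 − (1 − q)(1 − f × retreatment rate). The comparison rule counts any PASI loss and censors at retreatment if the threshold is held.

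With q = 10%:

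| f | Retreated while holding (active / withdrawal) | Recorded events (active / withdrawal) | Rejects: SAP rule | Rejects: censoring |
|---|---|---|---|---|
| 10% | 1.0% / 2.5% | 10.9% / 12.3% | 5.9% | 5.1% |
| 25% | 2.5% / 6.3% | 12.3% / 15.6% | 10.2% | 4.6% |
| 50% | 5.0% / 12.5% | 14.5% / 21.3% | 29.7% | 4.3% |
| 100% | 10% / 25% | 19.0% / 32.5% | 73.9% | 4.5% |

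For the same f, the SAP rule rejects in 6.0%, 16.2%, 40.3% and 81.3% of trials with q = 5%, and in 5.5%, 8.8%, 21.2% and 57.4% with q = 20%. Censoring stays between 4.1% and 5.9% throughout. The Monte Carlo standard error at 5% is √(0.05 × 0.95/2000) ≈ 0.5 points.

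**4. A limit on these rows.** Patients retreated after failing the threshold are part of q, so equal loss requires (1 − f) × 25% ≤ q in the withdrawal arm. At q = 10% this needs f ≥ 1 − 0.10/0.25 = 60%; at q = 20%, f ≥ 20%. The lower-f rows at q = 10% therefore fit equal PASI loss only if fewer than 25% are retreated. The rejection rate would then be lower, so those rows are best read as upper figures. The q = 20% rows at f of 25% and above meet the condition.

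**The case against.** The strongest defence is that the rule is a deliberate composite. Protocol 7.5 already treats retreated patients as non-responders, and its amendment log explains that retreatment reflects lack of efficacy. SAP 10.1.4 applies this to response by visit, including PASI 75, 90 and 100 at Week 52, and SAP 10.1.3 carries the same idea into the time-to-event analysis. Protocol 7.3.3 does not name retreatment and leaves further information to the analysis plan. Censoring at relapse is probably informative, so its near-5% rejection rate, obtained under assumed independence, is a best case.

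Much of this stands. The composite is defensible, and replacing it by censoring alone would exchange one weakness for another. But protocol 7.5 governs response by visit, not time to loss, and leaving details to the analysis plan does not license an event rule opposite to the one written. A composite also needs to be named as one.

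A second objection is that PASI and sPGA grade similar signs, so a 2.5-fold difference in relapse with no difference in PASI loss is a constructed null. That is right: the simulation shows what the test can do, not what this trial should be expected to show.

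**Conclusion.** The point holds for PASI 50 and PASI 75, and for PASI 90 in limited disease. For these, the SAP analysis is of loss of PASI X or retreatment, it conflicts with protocol 7.3.3(d), and SAP 14.1 does not declare the change. Its size depends on the share of retreated patients who still hold the threshold, which the documents do not give. With 10% common loss, rejection runs from about 6% at a share of 10% to 74% at 100%, under a retreatment difference that is probably too large.

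A reader might infer more than the documents support:

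- **That all four thresholds are affected.** PASI 100 cannot be.
- **That a false rejection rate of 74% to 81% is to be expected.** Those figures require every relapsing patient to keep the threshold. At baseline 12, lower-limb disease has already failed PASI 75 and four-region disease has failed PASI 50, and both rules then record an event.
- **That the PASI curves add nothing to time to relapse.** They also count PASI loss in patients who never reach sPGA 3.
- **That the main conclusions are at risk.** These are further endpoints outside the hierarchy in SAP 10.4, so primary and ranked results are not affected.

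**What to change.** Reconcile SAP 10.1.3 with protocol 7.3.3(d) and list the change in SAP 14.1. For PASI 50, 75 and 90:

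- label the current analysis *time to loss of PASI X or retreatment*;
- report the events by type in each arm (PASI loss, discontinuation for worsening disease, retreatment with the threshold still met);
- present the protocol's censoring rule beside it, using the PASI at relapse visit R1 before retreatment: an event if the threshold is failed, otherwise censored at that measurement.

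Leave the sPGA endpoints unchanged.

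No new data are needed. Flow Charts 2 and 3 schedule PASI at R1, protocol 6.2.2 places treatment-period assessments before dosing, and the Part B window in SAP Table 8 runs to the first retreatment date. The cost is a few lines of SAP text and one extra analysis per threshold. Because the censoring may be informative, neither curve should be read alone.

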10.1.4 Missing Data Imputations

Missing data will be imputed using the following methods for the efficacy analyses:

- Non-Responder Imputation (NRI): the NRI analysis will categorize any subject who does not have evaluation during a specific visit window as a non-responder for that visit. The only exception is when the subject is a responder both before and after a specific visit window, then the subject will be categorized as a responder for the visit. Only observations within the same analysis period will be used except for summary of ITT_A2 from ARM 1, where subjects' observation from Part A1 can be used since the treatment is the

same. The NRI will be the primary approach in the analyses of categorical variables.

- Last Observation Carried Forward (LOCF): The LOCF analyses will use the last observed non-missing evaluation (last completed non-missing evaluation, from composite endpoint) from the previous visit within the particular period for efficacy measures assessed to impute missing data at later visits in the same period. Baseline efficacy evaluations will not be carried forward. Of note, post-baseline observations from Part A1 can be carried forward to ITT_A2 subjects from ARM 1 since treatment is the same. LOCF will be the primary approach in the analyses of continuous variables, and the secondary approach in the analysis of categorical variables.
- As-Observed Cases (OC): The as-observed analysis will not impute values for missing evaluations, and thus a subject who does not have an evaluation on a scheduled visit will be excluded from the as-observed analysis for that visit. As-observed analysis will be the secondary approach in the analysis of continuous variables.
- Multiple Imputation (MI): The MI will be used as sensitivity approach to impute missing data in primary and ranked secondary endpoints. The variables to be included in the imputation model are listed below. If MI is not applicable due to the nature of our data (e.g., MCMC algorithm does not converge), logistic regression or mixed effect model repeat measurement (MMRM) methods will be applied as sensitivity approach, whichever applicable.

The Multiple Imputation analysis will be carried out in three steps.

- Imputation of missing data. The imputation will be generated for each efficacy endpoint measurement. The variables to be included in the imputation model are: Baseline disease severity (PASI and sPGA), Baseline weight (continuous variable), treatment group, actual prior TNF antagonist exposure, and measurements at each visit from randomization (or re-randomization) up to the end of the analysis period. For each endpoint, 20 'complete' datasets will be generated using SAS PROC MI. The imputed post-baseline measurements

will be rounded to the same precision as the observed data before the determination of responder status (e.g., PASI 90).

- Analysis of imputed data sets. A CMH test, stratified by stratification factors, will be used to analyze categorical endpoints in each imputed dataset.
- Synthesis of imputation and analysis results. SAS PROC MIANALYZE will be used to generate the final inferences of the risk difference between treatment groups.

Of note, subjects who discontinued due to AE of "Worsening of disease under study," or received retreatment with risankizumab for relapse during Part B, will be counted as non-responders in all visits thereafter in the NRI and MI analyses, and will have their last observation prior to discontinuation or retreatment with risankizumab carried forward in the LOCF analyses.

